We will recruit patients undergoing 1 of 2 procedures (either bariatric surgery or catheter-based atrial fibrillation ablation) at Yale-New Haven Hospital. Bariatric surgical patients undergoing sleeve gastrectomy or gastric bypass only will be enrolled. Patients will be contacted through their treating/implanting physician's office via phone around the same time that their final pre-operative appointment is confirmed by an automated system (2 days prior). At this time, the office staff will inform eligible patients that if they are interested, a research associate (RA) will be onsite the day of their appointment to discuss participating in a study looking to monitor post-procedure safety and effectiveness. Eligibility will be determined by the cardiac electrophysiologist stating that the patient is being seen pre-procedurally for catheter ablation of atrial fibrillation or the bariatric surgeon stating that the patient is being seen pre-operatively for sleeve gastrectomy or gastric bypass. On the phone call, patients will be informed that participation is optional but if they would like to learn more that they should plan to be at the office for additional time and to bring their smartphone and MyChart login information, any phone account passwords, and a recent prescription if possible (please see Appendix for script). Patients not reached will have a message left stating the same. If a patient has been deemed eligible by their treating physician but is not scheduled to be seen in office again prior to their procedure, the RA may reach out directly via phone to ask if the patient would be interested in

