Because the mobile health platform (Hugo) obtains patient data through patient portals, all patients who connect will need a YNHH MyChart account. The RA will assist the patients in creating a MyChart account. On a desktop computer, the RA will log into her YNHH Epic Hyperspace account. She will look up the given patient and then enable the patient to obtain a MyChart account through the "Launch MyChart Signup" functionality. The patient will then confidentially create a MyChart account (the RA's YNHH Epic Hyperspace account is automatically locked) by entering his/her own username, password, and retyping the password. Once the patient has completed the MyChart sign-up process, then the RA will assist the patient in creating and activating an account for the mobile health platform, Hugo, on the patient's personal smartphone. Some patients may need to reset their MyChart password, and the RA will enable them to do so. Some patients may have forgotten their MyChart username, and the RA will be able to provide this information to them through the "Launch MyChart Signup" functionality. The RA will also assist the patient in connecting their mobile health platform account with other health systems where they have received care by showing the study participant how to enter their patient portal credentials, provided that these health systems are connected to the mobile application, as well as to pharmacy portals where they have received medications (if that includes CVS or Walgreens). Patients will also receive a syncable device relevant to their procedure (i.e. AliveCor Kardia Mobile for catheter ablation of atrial fibrillation or Nokia Body digital weight scale for bariatric surgery patients and Fitbit for all patients). At this time, patients will also complete their pre-operative/baseline questionnaires so that the RA is present to assist them. The RA will also ask patients to obtain and upload their continuity of care document (CCD) if they receive care in a health system that is not connected to Hugo, at both enrollment and again at 8 weeks; the RA will also ask patients to obtain credentials, if necessary, and connect portals to health systems where they receive care that are connected to Hugo but were unable to connect at enrollment. Patients will also receive a follow-up email from the RA that includes user guides for the devices they have received (Appendix).

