- 2. Patient reported outcome measures (PROMs), prompted via mobile-friendly questionnaires to study participants
- 3. Data from syncable devices provided to patients (Fitbit and Nokia Body digital weight scale for sleeve gastrectomy and gastric bypass patients; Fitbit and AliveCor, Kardia Mobile for catheter-based atrial fibrillation ablation patients)
- 4. Medication data from 2 major pharmacy chains (CVS or Walgreens)

Additionally, patients will be contacted by the RA via phone at 2 months to ascertain the health systems in which they sought care and the Hugo platform will be checked to ensure that data from those health systems is included (and patients will be asked to link those health systems or provide data, as appropriate). Multiple attempts will be made to contact patients if they are not contacted on the first attempt.

Bariatric surgery (either Sleeve Gastrectomy or Gastric Bypass) Patients Only

1. All patients enrolled in the study will then be asked to answer questions administered using the mobile health platform at baseline (pre-procedure), 1 week, 4 weeks, and 8 weeks post-procedure using validated symptom questionnaires from the National Institute of Health's PROMIS® (Patient-Reported Outcomes Measurement Information System), which we will adapt to a mobile format (See Appendix for original paper and mobile versions). These will ask about global health, pain, gastroesophageal reflux, nausea and vomiting, diarrhea,

constipation, and sleep. In addition, every Monday and Thursday for a total of 10 times immediately following their procedure, patients will be asked 2-4 questions on a visual analog scale related to pain and appetite. Please see Appendix for questionnaires as inputted into the mobile health platform as well as the original paper version.

- 2. We will attempt to sync the following data from syncable devices for study participants:
 - Fitbit (Ambulation, heart rate, and other activity), synced weekly
 - Digital weight scale, synced weekly
- 3. We will attempt to retrieve the following data from the electronic health record into Hugo for study participants:

Pre-procedural information

- Co-morbidities, prior surgeries, medications, and allergies
- Physician outpatient notes, including History & Physical

Intra- and post-procedural information during index hospitalization

- Duration of hospitalization
- Co-incident procedures at the time of sleeve gastrectomy or gastric bypass
- Re-operation or re-intervention
- Vital signs

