As each patient completes 8 weeks of follow-up, all patient data will be sent to the Mayo Clinic, where an analyst will clean and curate the data made available through the Hugo platform. The analyst will then send the cleaned data for the YNHH patients to the Yale investigator team. The RA will then confirm the primary diagnoses in the YNHH Electronic Medical Record (EMR) for physician visits, emergency department visits, and inpatient admissions during the 8-week period by examining and comparing to the research database to determine if any encounters or diagnoses are missing in the research database.

The data points that we will validate in the Hugo Research Database from the YNHH Epic EMR will be:

- Encounter date
- Encounter type
- Primary diagnosis for encounter

We will also note if any additional physician visits, emergency department visits, and inpatient admissions are seen in either system (in the case of additional points in Hugo, we will also determine if they are from another health system). If any diagnoses are missing in the Hugo Research Database, we will determine from which visit that they were missing.

In addition, we will examine YNHH EMR data to determine what new medications were prescribed at discharge, and then we will examine pharmacy data to determine which of these prescriptions were filled by the patient.

Finally, at the end of the pilot study (i.e. at 8 weeks post-procedure), study participants will be called by the RA and asked to complete a close-out questionnaire (see Appendix) to determine their satisfaction with the process of answering queries and provide the opportunity for them to offer comments and suggestions for

improvement. They will also be asked at what health systems they received care over the past 8 weeks (including hospitalization, emergency department visit, repeat procedure), to assess if all pertinent data was captured in Hugo.

Close-Out Questionnaire, whereby study participants are called by RA at 8 weeks on a HIPAA-protected secure phone line and asked:

- 1. How was your overall experience using this technology (open-ended)?
- 2. How long did it take you, on average, to answer the questions that you were sent weekly?
- 3. How was the experience of answering questions (open-ended)?
- 4. Did you have any of the following in the past 8 weeks:
 - a. emergency department visit
 - b. admission to a hospital
 - c. re-operation
 - d. major complication

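### Fills of discharge prescriptions are read from CVS/Walgreens accounts linked before the procedure, and no visible later contact asks which pharmacy dispensed them, so fills elsewhere may be missed

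*Protocol*

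**What the plan says.** All of the relevant text is in the Protocol, Section I, item 4 (Research Plan), unless noted.

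- **The task.** After follow-up, new discharge medications are taken from the Yale electronic record, "and then we will examine pharmacy data to determine which of these prescriptions were filled by the patient".
- **The source.** The fourth of the four data sources is "Medication data from 2 major pharmacy chains (CVS or Walgreens"). The procedure-specific lists and Section IV, item 1 name no other dispensing source.
- **How accounts are linked.** At the set-up visit the research associate helps the patient connect the platform to other health systems "as well as to pharmacy portals where they have received medications (if that includes CVS or Walgreens"). The timing is before the procedure: "At this time, patients will also complete their pre-operative/baseline questionnaires so that the RA is present to assist them". On the earlier phone call patients are asked to bring "any phone account passwords, and a recent prescription if possible".
- **Later linking.** The associate will also ask patients to "connect portals to health systems where they receive care that are connected to Hugo but were unable to connect at enrollment". This concerns health systems.
- **Later contacts.** At the first, on the day after the procedure, the associate checks devices and answers questions. Then "patients will be contacted by the RA via phone at 2 months to ascertain the health systems in which they sought care". At the close-out call, "They will also be asked at what health systems they received care over the past 8 weeks". None of the six printed close-out items mentions pharmacies or fills.
- **Neighbouring steps.** The discharge-summary abstraction compares prescribed medications with those the patient received at discharge. The pharmacy fields to be obtained include active prescriptions, the amount dispensed, fill frequency and prescriber.

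**The concern.** The linked accounts reflect where patients obtained medicines in the past, fixed before any discharge prescription exists. A patient may have a new prescription dispensed somewhere else, for example at a pharmacy outside the two chains. The Protocol plainly sees this problem for medical care: at 8 weeks it asks where care was received and then requests a portal link or an uploaded care document. Pharmacy data are one of the four sources under test, but they get no corresponding check in the visible text.

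At stake is how a missing record is read. It may mean that the patient did not fill the prescription, or that the platform did not see the fill. These are different findings for a feasibility study: one is about patient behaviour, the other about capture. An analysis plan can choose a denominator or a label, but it cannot recover a dispensing location that nobody asked for.

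**Working it through.** **Step 1: the text.** The Protocol states no fill rate and no share of fills at a linked chain, so there is no figure to reproduce. The check is whether any visible step after discharge locates a fill at an unlinked pharmacy.

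| Step | What it covers | Locates fills elsewhere? |
|---|---|---|
| Linking at set-up | Past CVS/Walgreens use, before the procedure | No |
| Later portal connection, document upload | Health systems | No |
| Contact on the first day after the procedure | Devices, participant questions | No |
| Call at 2 months | Health systems | No |
| Close-out call, six printed items | Experience, events, health systems | No |
| Discharge-summary comparison | Medications received at discharge | Only what was received then |
| Pharmacy fields | Prescriptions and dispensing at the linked chain | Not directly; may settle some cases |

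Medication data from the patient portals are also collected, but the text does not present them as dispensing records.

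**Step 2: an illustration, with every input assumed.** It is limited to linked patients and to prescriptions not accounted for by the discharge comparison. Let f be the true fill proportion and c the share of fills made at the linked chain.

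- Recorded fill proportion = f × c.
- Filled elsewhere = f(1 − c).
- No dispensing record = 1 − fc.
- Share of missing records that were in fact filled elsewhere = f(1 − c)/(1 − fc).

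| | f = 70% | f = 80% | f = 90% |
|---|---|---|---|
| c = 100% | 0% | 0% | 0% |
| c = 90% | 0.07/0.37 = 19% | 0.08/0.28 = 29% | 0.09/0.19 = 47% |
| c = 70% | 0.21/0.51 = 41% | 0.24/0.44 = 55% | 0.27/0.37 = 73% |

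For the under-count itself, take f = 90%. The recorded proportion is 90% at c = 100%, 0.90 × 0.90 = 81% at c = 90%, and 0.90 × 0.70 = 63% at c = 70%. In the other direction, a recorded 60% fits a true 60% (c = 100%), 0.60/0.80 = 75% (c = 80%) or 100% (c = 60%).

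**Step 3: what the illustration leaves out.** It treats each prescription as having a dispensing record or none. If the pharmacy fields show a prescription on file but never dispensed, that case points to non-filling at the linked chain and leaves the ambiguous group. This makes the group smaller, but it does not identify the prescriptions filled elsewhere. The span in the table reflects the chosen grid and is not an estimate for this study.

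**The case against.** The strongest case on the other side has five parts.

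1. **Nothing is misstated.** The Protocol does not say that a prescription without a record counts as unfilled, and its list of metrics contains no fill rate. A reader might infer such a rule from the stated aim, but the text does not support it. This stands, and it limits the point to what the planned data can show.
2. **The two outcomes are not always indistinguishable.** A reader might infer that unfilled and filled-elsewhere prescriptions can never be separated. That goes too far. The prescription-level fields may show a prescription held but not dispensed, and the discharge comparison may account for items received at discharge. This stands in part: the documents do not say whether undispensed prescriptions appear in the pharmacy data, and the discharge comparison does not reach later fills at other pharmacies.
3. **Incomplete capture is what the pilot studies.** Both aims describe obtaining pharmacy data, and the two-chain limit is stated openly. True, but without knowing where fills took place, a missing record cannot be attributed either to failed capture or to non-filling.
4. **The close-out questionnaire is in an Appendix that is not shown.** A pharmacy question there cannot be excluded. The six items printed in the text contain none.
5. **Labelling belongs in an analysis plan.** The choice of label and denominator does. The collection of the dispensing location does not.

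**Conclusion.** The point holds in limited form. The data planned in the visible text show which discharge prescriptions were recorded as filled at a linked CVS/Walgreens account. They do not fully support a determination of which were filled. A prescription in a linked patient that is absent from the pharmacy data, and unexplained by the discharge comparison, stays ambiguous unless the other pharmacy fields settle it.

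Patients with no linked account are a separate matter: they can be identified from set-up, and their fills are simply not ascertainable from this source.

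The size of the under-count is unknown; the percentages above rest wholly on assumed inputs. The importance is minor. The check is secondary and descriptive, covers 30 Yale patients (Section I, item 6), and sits in a feasibility pilot without a clinical primary outcome (Section I, item 13). The conclusion assumes that the Appendix questionnaire adds no pharmacy item.

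**What to change.** **Data collection.** For close-out calls still to be made, add one item after question 6: *7. Did you fill the prescriptions you were given at discharge and, if so, at which pharmacy?* This mirrors the existing check on health systems. If the Appendix version already contains such an item, print it with the six items in the Research Plan.

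**Reporting, in all cases.** Describe the result as a fill recorded at a linked CVS/Walgreens account. Report prescriptions of unlinked patients, and those the patient says were filled at an unlinked pharmacy, as not ascertainable from pharmacy data and not as unfilled. The denominator can be set in the analysis plan.

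**Cost.** One question on a call already planned, with no added visit or staff. The downsides are reliance on recall at 8 weeks and a smaller assessable denominator. The question helps only participants not yet closed out. The Protocol is dated September 24, 2018 and expected completion by August 2018, so few or no calls may remain; the reporting change applies either way.

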Specific Aim 1: To pilot test the feasibility of using this mobile health platform for post-market surveillance of patients after sleeve gastrectomy or gastric bypass by describing enrollment times, patient participation, dropout, completion of patient-reported outcome measure queries, syncing of mobile device data, obtaining of electronic medical record data, obtaining of pharmacy data, and user satisfaction and burden.

Specific Aim 2: To pilot test the feasibility of using this mobile health platform for post-market surveillance of patients after catheter-based atrial fibrillation ablation by describing enrollment times, patient participation, dropout, completion of patient-reported outcome measure queries, syncing of mobile device data, obtaining of electronic medical record data, obtaining of pharmacy data, and user satisfaction and burden.

2. **Probable Duration of Project:** State the expected duration of the project, including all follow-up and data analysis activities.

The project is expected to be completed no later than August 2018 with enrollment beginning in February 2018. Recruitment for patients is expected to take 2-4 months depending on the implanting physicians' schedules, with monitoring of each patient lasting 8 weeks post procedure. As each patient's 8-week post-operative period is concluded, we will begin to clean, review and verify the data as it is received from the Hugo Platform on a rolling basis.

3. **Background:** Describe the background information that led to the plan for this project. Provide references to support the expectation of obtaining useful scientific data.

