- Physician outpatient notes, including History & Physical

Intra- and post-procedural information during index hospitalization

- Duration of hospitalization
- Co-incident procedures at the time of atrial fibrillation ablation
- Re-intervention or other procedures (pericardiocentesis, cardioversion)
- Vital signs
- All associated secondary diagnoses during incident hospitalization
- Transfer to intensive care unit
- Post-operative imaging tests obtained (e.g. CT scans)
- Physician notes, including Operative Report and Discharge Summary

Post-procedural encounters after hospital discharge for 8 weeks

- Number of encounters
- Encounter type (e.g. outpatient visit, inpatient visit, labs, imaging)
- Diagnoses associated with encounters
- Physician notes
- Lab tests and Imaging test results
- 4. We will test the feasibility of obtaining medication data from major pharmacy chains (Walgreens or CVS), including active prescription names, formulations and dosages, days' supply or # dispensed, frequency of fills, and prescriber.

Patients will receive automatic reminders to complete questionnaires daily for 2 days via email. Similarly, patients will receive automatic reminders to sync their AliveCor and Fitbit weekly for 2 days after the planned sync date.

The metrics we plan to collect are as follows:

A. Enrollment-related

- Number of people asked for study participation and number enrolled
- Number of study participants who required assistance setting up Yale-New Haven Hospital or Mayo Clinic portals
- Number who had YNHH or Mayo portals who could not be enrolled (e.g. because they had forgotten password, no space on mobile device, technical glitch, etc)
- Time to set up new Hugo account and enroll patient in study
- Total enrollment time (from initiation of conversation with RA to completion of connecting health system portals)

B. PROM-related (for all PROMs)

- Rate of opening PROM emails
- Rate of PROM survey response
- Mean time to PROM survey response
- Proportion of items completed
- Proportion of people who completed PROM survey after initial email or after 1 reminder

C. Mobile Device-related

• Proportion of people who sync their devices (AliveCor, digital scale, and FitBit) at 1, 2, 3, 4, 5, 6, 7, 8 weeks

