(http://hugophr.com/security), its Privacy Notice (http://hugophr.com/security), and Terms of Service (http://hugophr.com/terms-of-service)

Participants will undergo the possible inconvenience of filling out electronic patient-reported outcome measure surveys, which should take approximately 60 minutes for the longer surveys (at baseline, 1 week, 4 weeks, and 8 weeks) and 15 minutes for the short surveys every Monday and Thursday a total of 10 times. Participants will also experience the possible inconvenience of wearing a Fitbit for extended periods of time as well as the possible inconvenience of utilizing and syncing the Kardia Mobile or Nokia Body Scale once a week. The estimated time required to sync the weight scale weekly for 8 weeks is 30 minutes, to sync the AliveCor weekly for 8 weeks is 30 minutes, and to sync the Fitbit weekly for 8 weeks is 15 minutes.

Although the Fitbit has been deemed a 'Low-Risk Device' by the FDA⁷ and is therefore not deemed medical grade⁸, there is the risk of inaccuracy in Heart Rate measurements. According to the Fitbit terms of service, found at www.fitbit.com/legal/terms-of-service, "The accuracy of the data collected and presented through the Fitbit Service is not intended to match that of medical devices or scientific measurement devices." The AliveCor Kardia Mobile device has been approved by the FDA as a 510k device since January 2015. In one published study of patients post-atrial fibrillation ablation that tested use of the AliveCor, only 2% of patients found it difficult to use⁹. However, as noted above, we will clearly state to the patients that this study should in no way impact their regular care plans.

11. Minimizing Risks: Describe the manner in which the above-mentioned risks will be minimized.

All patient data will be collected, handled, and stored according the most rigorous accepted standards. Staff involved in the study will be appropriately trained to maximize data security and technical systems will meet or exceed requirements imposed by HIPAA. Sensitive information will always be encrypted in transit (using secure file transfer protocols when data is obtained at Yale from the Mayo Clinic team that is cleaning and curating the data) and at rest. Paper documents at YNHH/CORE will be scanned into and saved onto a secure server. Once documents are scanned, the original documents will be shredded using a secure document destruction service.

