Since the data obtained are from broad health characteristics from personal health records that do not target any particular sensitive research areas, a CoC has not been obtained.

SECTION V: POTENTIAL BENEFITS

Potential Benefits: Identify any benefits that may be reasonably expected to result from the research, either to the subject(s) or to society at large. (Payment of subjects is not considered a benefit in this context of the risk benefit assessment.)

Individuals who participate in this study will have access to their health data along with the choice and ability to share it with researchers. Those who choose to share their information will help create a more robust research database, will pioneer a new method for data collection that will enable researchers to continue to strive for better health outcomes, and advance the understanding of health and disease. Participants will also have the option of continuing access to their data at the end of the study, if they so wish, and receive updates to the sync for science platform. Using the provided syncable devices, participants may also gain additional awareness and information regarding their health and fitness.

SECTION VI: RESEARCH ALTERNATIVES AND ECONOMIC CONSIDERATIONS

1. Alternatives: What other alternatives are available to the study subjects outside of the research?

The alternative to participating in the proposed study is to not participate. Participation and non-participation will have no impact on the course of treatment that the patient will receive.

2. **Payments for Participation (Economic Considerations):** Describe any payments that will be made to subjects, the amount and schedule of payments, and the conditions for receiving this compensation.

Patients will receive a stipend for their time contributed as part of this study. Estimated hourly stipend based on the average minimum wage in Connecticut (\$10) will be provided. This stipend will cover the consent process, initial set up and baseline questionnaire (4 hrs), longer questionnaires provided at, 1-, 4-, and 8-weeks (1 hour each), short questionnaires provided every Monday and Thursday a total of 10 times (15 minutes each), along with the time it takes to sync and use the provided devices (0.5 hrs per week for AliveCor and weight scale; 0.25 hrs per week for Fitbit). The total estimated maximum time is 15.5 hours.

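### Close-out item 2 asks for one average time to answer questions sent weekly, but no survey is weekly, so the unit is unclear and the long surveys have no clear completion-time measure

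*Protocol*

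**What the plan says.** All of this is in the Protocol.

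- **Item 2 (Section I.4, Close-Out Questionnaire).** The research associate phones participants at 8 weeks and asks "How long did it take you, on average, to answer the questions that you were sent weekly". It is a single question that calls for a single average. Items 1 and 3 are open-ended questions about experience.
- **Survey schedule (Section I.4, both procedure groups).** Short visual analog surveys go out "every Monday and Thursday for a total of 10 times immediately following their procedure". The longer questionnaires are set at baseline and at 1, 4 and 8 weeks.
- **What is weekly.** In Section I.4 the planned weekly activity is device syncing, for example "Fitbit (Ambulation, heart rate, and other activity), synced weekly".
- **Estimated times.** Section I.10 (Risks) gives "approximately 60 minutes for the longer surveys (at baseline, 1 week, 4 weeks, and 8 weeks) and 15 minutes for the short surveys". Section VI.2 (Payments) uses the same basis for the stipend: "short questionnaires provided every Monday and Thursday a total of 10 times (15 minutes each").
- **Aims and metrics.** Specific Aims 1 and 2 both end with "user satisfaction and burden". The only other survey-time measure is "Mean time to PROM survey response", in the PROM-related metrics of Section I.4.
- **Health-system question.** The paragraph before the questionnaire says "They will also be asked at what health systems they received care over the past 8 weeks", and item 4 also looks back 8 weeks. Item 6 looks back 60 days. Earlier in Section I.4, the phone contact on health systems is placed at 2 months.

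**The concern.** Item 2 describes a survey that the schedule does not contain. It therefore fixes neither the survey type nor the unit, which could be one survey or one week. A reply of 30 minutes could mean two short surveys in a week at exactly the estimate, or one short survey at twice the estimate.

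This matters because burden is one of the things the pilot sets out to describe, and item 2 is the only close-out question on answering time. It is also the natural check on the 60- and 15-minute estimates behind the burden disclosure and the stipend. As worded, it cannot confirm or correct either one. If most participants take it to mean the short surveys, the surveys with the larger share of estimated time are not covered.

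**Working it through.** **Inputs.** Long survey 60 minutes, short survey 15 minutes (Section I.10). Three long and ten short surveys after the procedure (Sections I.4 and VI.2). Section VI.2 counts the baseline survey inside a 4-hour set-up block.

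**1. The plan's own total.** Section VI.2 states a maximum of 15.5 hours. Set-up and baseline 4, plus long surveys 3 × 1, plus short surveys 10 × 0.25, plus syncing 8 × (0.5 + 0.25), gives 4 + 3 + 2.5 + 6 = 15.5 hours. It reproduces exactly, which confirms the survey counts and times used below.

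**2. Is any survey weekly?** Ten short surveys at two per week span 10 / 2 = 5 weeks. Long surveys fall at weeks 1, 4 and 8. Neither type goes out once a week.

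**3. What item 2 could return if every estimate were exactly right.**

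| Reading | Arithmetic | Minutes |
|---|---|---|
| Per short survey | 15 | 15 |
| Short surveys per week | 2 × 15 | 30 |
| Per long survey (less natural) | 60 | 60 |

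Other averages fall between these limits. The mean over all 13 post-procedure surveys is (3 × 60 + 10 × 15) / 13 = 330 / 13 = 25.4 minutes. The mean per week over 8 weeks is 330 / 8 = 41.25 minutes.

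**4. Share of survey time.** Long surveys: 180 / 330 = 55%. Short surveys: 150 / 330 = 45%.

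**5. Timing at the call.** Assume short surveys start on the first Monday or Thursday after the procedure day. The first then falls on day 1 to 4, depending on the procedure weekday. The tenth falls 31 days later if the first is a Monday and 32 days later if it is a Thursday. Over all seven procedure weekdays, the tenth falls on day 32 to 35. At a call on day 56, the last short survey is 56 − 35 = 21 to 56 − 32 = 24 days past, while the 8-week long survey is due at that same time. This is why some participants may answer about the long one.

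**6. Look-back in item 6.** Eight weeks is 56 days, and 60 − 56 = 4. On a day-56 call, the item 6 window opens 4 days before the procedure. Two calendar months are 59 to 62 days, so a contact at 2 months is 3 to 6 days later than one at 8 weeks.

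**The case against.** The strongest reply is that this is loose wording in a descriptive question. The short surveys are the only ones sent in successive weeks, so a listener would probably think of them, and the remaining doubt is mainly 15 against 30 minutes. The research associate asks live by phone and can clarify. The Appendix form, which is not shown, may be clearer. This largely stands and keeps the point minor. However, Section I.4 lists the items as what participants are asked, and it gives the caller no instruction to clarify the unit.

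A second reply is that the time-to-response metric covers all PROMs and might mean completion time. It sits among email opening, response rates and reminders, so delay until response is the likelier meaning. The protocol does not define it. If completion time is meant, the part about the long surveys falls away.

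Four stronger readings are tempting, and the documents do not support them:

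- A reader might take 90 minutes (two short surveys plus one long) as the upper limit. That is the total for weeks 1 and 4, not an average, and item 2 asks for an average.
- A reader might infer that the answers are bound to be unusable. That assumes the caller records a bare number, which the protocol does not say.
- A reader might infer that burden goes unmeasured. Dropout, participation, response rate, items completed, reminder use and open comments are also collected.
- A reader might infer that the 60-day window loses data, or that 2 months is a third look-back. A 60-day window at day 56 contains the whole 8-week period, and 2 months is a contact time that may loosely label the same call.

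**Conclusion.** The point holds as a minor flaw in how a question is worded. As listed in Section I.4, item 2 refers to no survey in the schedule and leaves the unit open. At the protocol's own estimates, the likely reading gives 15 or 30 minutes, and 60 if a participant answers about the long survey. The long surveys, 55% of estimated post-procedure survey time, have no clear completion-time measure. That last part depends on the time-to-response metric meaning delay.

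The item 6 mismatch is only an inconsistency: 4 days in the look-back and 3 to 6 days in the call time, with no post-procedure care missed at a day-56 call.

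Confidence is moderate, because the Appendix form may be worded differently. The pilot has no clinical primary outcome (Section I.13), and nothing beyond the descriptive account of burden is affected.

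**What to change.** Replace item 2 with two questions: minutes per Monday/Thursday survey, and minutes per 1-, 4- and 8-week survey. Each then has a stated survey type and unit, and can be set against the 15- and 60-minute estimates. If the time-to-response metric is meant as completion time, saying so would cover the long surveys in part.

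Align the look-back in item 6 with item 4 and with the description of the call, using the 8-week period that the medical-record comparison already uses. Give one call time in both places in Section I.4 where the phone contact is described. Check the Appendix form for the same wording.

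The cost is one more question in an existing phone call and a few words of editing. Answers will still rest on recall.
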